### 90th and 95th PERCENTILE BLOOD PRESSURE BY PERCENTILE HEIGHT IN BOYS AGE 1-17 YEARS

Age (Year)	BP Percentile ↓	Systolic BP (mmHg)							Diastolic BP (mmHg)						
		Percentile of Height							Percentile of Height						
		5th	10th	25th	50th	75th	90th	95th	5th	10th	25th	50th	75th	90th	95th
1	90th	94	95	97	99	100	102	103	49	50	51	52	53	53	54
	95th	98	99	101	103	104	106	106	54	54	55	56	57	58	58
2	90th	97	99	100	102	104	105	106	54	55	56	57	58	58	59
	95th	101	102	104	106	108	109	110	59	59	60	61	62	63	63
3	90th	100	101	103	105	107	108	109	59	59	60	61	62	63	63
	95th	104	105	107	109	110	112	113	63	63	64	65	66	67	67

4	90th	102	103	105	107	109	110	111	62	63	64	65	66	66	67
	95th	106	107	109	111	112	114	115	66	67	68	69	70	71	71
5	90th	104	105	106	108	110	111	112	65	66	67	68	69	69	70
	95th	108	109	110	112	114	115	116	69	70	71	72	73	74	74
6	90th	105	106	108	110	111	113	113	68	68	69	70	71	72	72
	95th	109	110	112	114	115	117	117	72	72	73	74	75	76	76
7	90th	106	107	109	111	113	114	115	70	70	71	72	73	74	74
	95th	110	111	113	115	117	118	119	74	74	75	76	77	78	78
8	90th	107	109	110	112	114	115	116	71	72	72	73	74	75	76
	95th	111	112	114	116	118	119	120	75	76	77	78	79	79	80
9	90th	109	110	112	114	115	117	118	72	73	74	75	76	76	77
	95th	113	114	116	118	119	121	121	76	77	78	79	80	81	81
10	90th	111	112	114	115	117	119	119	73	73	74	75	76	77	78
	95th	115	116	117	119	121	122	123	77	78	79	80	81	81	82
11	90th	113	114	115	117	119	120	121	74	74	75	76	77	78	78
	95th	117	118	119	121	123	124	125	78	78	79	80	81	82	82
12	90th	115	116	118	120	121	123	123	74	75	75	76	77	78	79
	95th	119	120	122	123	125	127	127	78	79	80	81	82	82	83
13	90th	117	118	120	122	124	125	126	75	75	76	77	78	79	79
	95th	121	122	124	126	128	129	130	79	79	80	81	82	83	83
14	90th	120	121	123	125	126	128	128	75	76	77	78	79	79	80
	95th	124	125	127	128	130	132	132	80	80	81	82	83	84	84
15	90th	122	124	125	127	129	130	131	76	77	78	79	80	80	81
	95th	126	127	129	131	133	134	135	81	81	82	83	84	85	85
16	90th	125	126	128	130	131	133	134	78	78	79	80	81	82	82
	95th	129	130	132	134	135	137	137	82	83	83	84	85	86	87
17	90th	127	128	130	132	134	135	136	80	80	81	82	83	84	84
	95th	131	132	134	136	138	139	140	84	85	86	87	87	88	89

Source: Adapted from: The Fourth Report on the Diagnosis, Evaluation, and Treatment of High Blood Pressure in Children and Adolescents; NIH Publication No. 05-5267.

## 6.5 Liver Function Abnormalities

For patients with observed worsening of serum liver tests considered related to regorafenib (i.e. where no alternative cause is evident, such as post-hepatic cholestasis or disease progression), the dose modification and monitoring advice in Table 6.6 should be followed.

Regorafenib is a UGT1A1 inhibitor. Mild, indirect (unconjugated) hyperbilirubinemia may occur in patients with Gilbert syndrome. Note in Table 6.6 that hyperbilirubinemia itself is not a reason for dose reduction. Patients with Gilbert syndrome who develop elevated transaminases should be managed as per the recommendations outlined for ALT/AST elevations.

**Table 6.5.1 Recommended measures and dose modification in case of drug-related liver function test abnormalities**

Observed elevations of ALT and/or AST	Occurrence	Recommended measures and dose modification
≤ 5 times upper limit of normal ULN (maximum Grade 2)	Any occurrence	Continue regorafenib or placebo treatment.  Monitor liver function weekly until transaminases return to < 3 times ULN (Grade 1) or baseline.
>5 times ULN to ≤ 20 times ULN (Grade 3)	1 st occurrence	Interrupt regorafenib or placebo treatment.  Monitor transaminases weekly until return to < 3 times ULN or baseline.  Restart: If the potential benefit outweighs the risk of hepatotoxicity, re-initiate regorafenib or placebo treatment, reduce dose by 40 mg (one tablet), and monitor liver function weekly for at least 4 weeks.
	Re-occurrence	Discontinue treatment with regorafenib or placebo permanently.
> 20 times ULN (Grade 4)	Any occurrence	Discontinue treatment with regorafenib or placebo permanently.
> 3 times ULN (Grade 2 or higher) with concurrent hyperbilirubinemia > 2 times ULN		Discontinue treatment with regorafenib or placebo permanently.  Monitor liver function weekly until resolution to < 3 times ULN or return to baseline.  Exception: patients with Gilbert syndrome who develop elevated transaminases should be managed as per the above outlined recommendations for the respective elevation of ALT and/or AST.

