### 5.4 Study drug administration

Regorafenib (or placebo) is administered as monotherapy during the study. For adults on the study, the starting dose is 160 mg daily for 3 weeks on, 1 week off, taken in the morning with a low-fat meal each day.

The medication should be taken within 8 hours of the same time each day, otherwise should be marked as a missed dose. One cycle is 28 days.

For adults, four 40 mg regorafenib or placebo tablets should be taken in the morning with approximately 8 fluid ounces (240 mL) of water after a low-fat (< 30% fat) breakfast. Some examples of low-fat breakfasts are:

- Two slices of white toast with 1 tablespoon of low-fat margarine and 1 tablespoon of jelly and 8 ounces (240 mL) of skim milk (approximately 319 calories and 8.2 g of fat).
- One cup of cereal, 8 ounces (240 mL) of skim milk, one piece of toast with jam (no butter or marmalade), apple juice, and one cup of coffee or tea (2 g fat, 17 g protein, 93 g of carbohydrate, 520 calories).

The medication will be taken in a similar fashion in pediatric patients (< 18 years). ... Pediatric patients on trial will receive tablets according to the dosing table below (Table 5.4). The starting dose is 82 mg/m^2 daily with the same 3 week on, 1 week off schedule as for adult patients. The regorafenib dose will be rounded to the nearest 20 mg and capped at 160 mg as with adult patients. The lowest permissible dose is 20 mg. The minimum body surface area to participate is 0.65m^2 and minimum weight is 15 Kg. (33 lbs.)

Table 5.4 – Pediatric Doses

	BSA > 0.65m 
Dose level 0 (standard starting dose)	82 mg/m  oral daily

For dose modifications, for adult and pediatric patients, refer to tables in Section 6 of the protocol.

Patients, or their guardians, should be instructed to record daily regorafenib or placebo dose on the Study Drug diary which will be provided to them (Appendix C).

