## **6. DOSING DELAYS/DOSE MODIFICATIONS**

### **6.1 Dose Reduction Levels**

**In adults, the starting dose of regorafenib is 160 mg once daily for Cohorts C, D and E. The starting dose for Cohorts A and B is 4 tablets of regorafenib or placebo daily.**

**For pediatric patients (< 18 years of age), the starting dose is 82 mg/m^2 (rounding to nearest 20 mg), with a maximum daily dose capped at 160 mg. Please refer to dosing table in Section 5.2.**

Study medication will be administered on a 3-weeks on, 1-week off schedule (3 weeks out of every 4).

Doses will be delayed or reduced for clinically significant hematologic and non-hematologic toxicities that are related to protocol therapy according to the guidelines shown in the Dose Delays/Dose Modifications table that follows. In general, this will mean clinically meaningful G 3 or worse toxicity, although clinically significant G 2 toxicity may qualify, according to the treating physician. Dose modifications will follow predefined dose levels. Dose adjustments for hematologic toxicity are based on the blood counts obtained in preparation for the day of treatment.

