**Table 6.1.1 Dose reduction levels – adult patients**

The modifications of regorafenib or placebo dosing will follow the following predefined dose levels:		
Dose level 0 (standard starting dose)	160 mg oral daily	Four 40 mg tablets of regorafenib or placebo
Dose level -1	120 mg oral daily	Three 40 mg tablets of regorafenib or placebo
Dose level -2	80 mg oral daily	Two 40 mg tablets of regorafenib or placebo

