**Table 6.1.2 Dose reduction levels – pediatric patients**

The modifications of regorafenib or placebo dosing will follow the following predefined dose levels:	
Dose level 0 (standard starting dose)	82 mg/m^2 oral daily, rounding to nearest 20 mg
Dose level -1	72 mg/m^2 oral daily, rounding to nearest 20 mg
Dose level -2	60 mg/m^2 oral daily, rounding to nearest 20 mg

If a subject experiences more than 1 toxicity, dose reduction should be according to the toxicity with the highest grade.

In the case of 2 or more toxicities of the same grade, the investigator may dose reduce according to that deemed most causally related to study treatment.

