## **6.2 Management of toxicity (other than hand-foot skin reaction, hypertension and LFT abnormalities)**

The table below outlines dose adjustments for **most hematologic and non-hematologic toxicities related to regorafenib** except hand-foot skin reaction (HFSR) and hypertension and LFT abnormalities.

In addition to these recommended dose modifications, subjects who develop diarrhea (see

Section 6.6), mucositis, anorexia or other events predisposing to fluid loss or inadequate fluid intake should be carefully monitored and rehydrated as clinically necessary. This is in order to minimize the risk of postural hypotension and renal failure.

**Table 6.2 Recommended dose modification for most toxicities, except hand-foot skin reaction, hypertension and ALT/AST/bilirubin**

NCI-CTCAE v 4.03 a	Dose Interruption	Dose Modification b	Dose for Subsequent Cycles
Grade (G) 0-2	Treat on time	No change	No change
G 3	Delay until $\leq$ G 2 c	Reduce by 1 dose level	If toxicity remains < G2, dose re-escalation can be considered at the discretion of the treating investigator. If dose is re-escalated and toxicity ( $\geq$ G3) recurs, institute permanent dose reduction.
G 4	Delay until $\leq$ G 2 c	At a minimum, reduce by 1 dose level.  Strongly consider permanent discontinuation for G4 events such as: gastrointestinal perforation/fistula, severe or life-threatening hemorrhage, reversible posterior leukoencephalopathy syndrome, or wound dehiscence.	

a. G: Grade; NCI-CTCAE = National Cancer Institute - Common Terminology Criteria for Adverse Events, version 4.03
 
b. Excludes alopecia, non-refractory nausea/vomiting, non-refractory hypersensitivity and nonclinical and asymptomatic laboratory abnormalities.
 
c. If no recovery after a 4 week delay, treatment should be permanently discontinued unless subject is deriving clinical benefit and is discussed with the SARC Medical Officer.
			

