**Table 6.4.2 Management of Treatment Emergent Hypertension for pediatric patients**

**Please refer to appendix:**

Grade (CTCAE v 4.03)	Antihypertensive Therapy	Regorafenib or placebo Dosing
Grade 1 If age ≤ 17 years: Asymptomatic, transient (< 24 hrs) BP increase > ULN; intervention not indicated. If age > 17	Consider increased BP monitoring; start anti-hypertensive medication if appropriate	No modification

years: (SBP 120-139 mmHg or DBP 80-89 mmHg)		
Grade 2 asymptomatic If age ≤ 17 years: Recurrent or persistent (≥ 24 hrs) BP > ULN; If age > 17 years: (SBP 140-159 mmHg or DBP 90-99 mmHg)	-If age ≤ 17 years: monotherapy indicated, -If age > 17 years: As in Table 6.5	Continue Study drug
Grade 2 symptomatic OR Grade 3: (> 17 years: SBP > 160 mmHg or DBP > 100 mmHg) requiring more than one drug or more intensive therapy than previously (all ages)	• Start or adjust anti-hypertensive medication as in table 6.5	• Hold study drug until symptoms resolve AND BP < 95th percentile ULN for age, height, and gender, if age ≤ 17 years; or BP < 160/90 mmHg if age > 17 years. Resume study at 100% (full) dose. If similar toxicity recurs, discontinue study drug.
Grade 4 (all ages) life threatening (eg, hypertensive crisis or malignant hypertension)	Per institutional guidelines	Discontinue study drug

**90th and 95th PERCENTILE BLOOD PRESSURE BY PERCENTILE HEIGHT IN  
GIRLS AGE 1-17 YEARS**

Age (Year)	BP Percentile	Systolic BP (mmHg)							Diastolic BP (mmHg)						
		Percentile of Height							Percentile of Height						
↓		5th	10th	25th	50th	75th	90th	95th	5th	10th	25th	50th	75th	90th	95th
1	90th	97	97	98	100	101	102	103	52	53	53	54	55	55	56
	95th	100	101	102	104	105	106	107	56	57	57	58	59	59	60
2	90th	98	99	100	101	103	104	105	57	58	58	59	60	61	61
	95th	102	103	104	105	107	108	109	61	62	62	63	64	65	65
3	90th	100	100	102	103	104	106	106	61	62	62	63	64	64	65

	95th	104	104	105	107	108	109	110	65	66	66	67	68	68	69
4	90th	101	102	103	104	106	107	108	64	64	65	66	67	67	68
	95th	105	106	107	108	110	111	112	68	68	69	70	71	71	72
5	90th	103	103	105	106	107	109	109	66	67	67	68	69	69	70
	95th	107	107	108	110	111	112	113	70	71	71	72	73	73	74
6	90th	104	105	106	108	109	110	111	68	68	69	70	70	71	72
	95th	108	109	110	111	113	114	115	72	72	73	74	74	75	76
7	90th	106	107	108	109	111	112	113	69	70	70	71	72	72	73
	95th	110	111	112	113	115	116	116	73	74	74	75	76	76	77
8	90th	108	109	110	111	113	114	114	71	71	71	72	73	74	74

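### For patients under 18, the flat 40 mg liver-test restart cut in Table 6.5.1 falls below paediatric level -1 at every BSA and often below level -2, and the rounded levels in Table 6.1.2 cannot replace it as they stand

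*Combined protocol and SAP*

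**What the plan says.** Section 5.4 refers adult and paediatric patients alike to the Section 6 tables for dose changes. The two groups have different dose ladders. Adults step 160, 120, 80 mg (Table 6.1.1), and level -1 is "Three 40 mg tablets of regorafenib or placebo". Patients under 18 step 82, 72, 60 mg/m², each "oral daily, rounding to nearest 20 mg" (Table 6.1.2), with a 160 mg cap. Section 5.4 adds: "The lowest permissible dose is 20 mg".

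Section 6.1 gives the general rule: "Dose modifications will follow predefined dose levels". Table 6.2 applies it to most toxicities; at Grade 3 the instruction is "Reduce by 1 dose level".

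Liver tests have their own rule. Section 6.5 says "the dose modification and monitoring advice in Table 6.6 should be followed"; the table meant is numbered 6.5.1. After a first Grade 3 ALT/AST rise, and if benefit is judged to outweigh risk, the site is to "re-initiate regorafenib or placebo treatment, reduce dose by 40 mg (one tablet), and monitor liver function weekly for at least 4 weeks". No age limit or paediatric alternative is given. Hypertension, by contrast, has a separate table, "Management of Treatment Emergent Hypertension for pediatric patients" (Table 6.4.2).

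**The concern.** The 40 mg step is the adult ladder written in milligrams. Applied to a child whose ladder is in mg/m² with 20 mg rounding, it need not match any paediatric level, and the smaller the child, the larger the proportional cut. Children are eligible for both open cohorts (D from age 5, E from age 10; minimum BSA 0.65 m²).

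The alternative is to follow Section 6.1 and step down one level in Table 6.1.2. The 82 and 72 mg/m² levels are so close that rounding can merge them. A child of 0.80 m² on 60 mg would then restart at 20 mg under Table 6.5.1 and at an unchanged 60 mg under Section 6.1, after the same Grade 3 liver event. The text does not say which rule prevails.

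**Working it through.** **Inputs.** Paediatric levels 82, 72 and 60 mg/m², rounding to 20 mg (Table 6.1.2); 160 mg cap, 20 mg floor and minimum BSA 0.65 m² (Section 5.4); adult levels 160/120/80 mg (Table 6.1.1); restart cut 40 mg (Table 6.5.1).

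**Adult check.** 160 - 40 = 120 mg, which is level -1. 120 - 40 = 80 mg, which is level -2. The rule fits the adult ladder exactly.

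**Paediatric formula.** Dose at level L = min(160, BSA × L rounded to the nearest 20 mg). Restart dose = level 0 dose - 40. BSA runs in 0.001 m² steps. The documents do not say how ties round; they are rounded up here. Rounding them down would move the band edges at 1.250 and 1.500 m² by 0.001.

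Example, 0.80 m²: 82 × 0.80 = 65.6, giving 60; 72 × 0.80 = 57.6, giving 60; 60 × 0.80 = 48, giving 40. Restart = 60 - 40 = 20 mg.

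Example, 0.90 m²: 73.8, giving 80; 64.8, giving 60; 54, giving 60. Restart = 80 - 40 = 40 mg.

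| BSA (m²) | Level 0 / -1 / -2 (mg) | Level 0 - 40 (mg) | Cut | Against level -2 | Level -1 = level 0? |
|---|---|---|---|---|---|
| 0.650-0.694 | 60/40/40 | 20 | 67% | below | no |
| 0.695-0.833 | 60/60/40 | 20 | 67% | below | yes |
| 0.834-0.853 | 60/60/60 | 20 | 67% | below | yes |
| 0.854-0.972 | 80/60/60 | 40 | 50% | below | no |
| 0.973-1.097 | 80/80/60 | 40 | 50% | below | yes |
| 1.098-1.166 | 100/80/60 | 60 | 40% | equal | no |
| 1.167-1.249 | 100/80/80 | 60 | 40% | below | no |
| 1.250-1.341 | 100/100/80 | 60 | 40% | below | yes |
| 1.342-1.499 | 120/100/80 | 80 | 33% | equal | no |
| 1.500-1.527 | 120/100/100 | 80 | 33% | below | no |
| 1.528-1.585 | 120/120/100 | 80 | 33% | below | yes |
| 1.586-1.805 | 140/120/100 | 100 | 29% | equal | no |
| 1.806-1.829 | 140/140/100 | 100 | 29% | equal | yes |
| 1.830-1.833 | 160/140/100 | 120 | 25% | above | no |
| 1.834-2.083 | 160/140/120 | 120 | 25% | equal | no |
| 2.084-2.166 | 160/160/120 | 120 | 25% | equal | yes |
| 2.167 and over | 160/160/140 or more | 120 | 25% | below | yes |

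In every row the restart dose is below level -1. In the two smallest starting-dose groups it is also far below 60 mg/m²: 20/0.853 = 23.4 to 20/0.650 = 30.8 mg/m², and 40/1.097 = 36.5 to 40/0.854 = 46.8 mg/m².

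**Frequency (paediatric phase I, Section 2.4.3).** Grade 3 or worse ALT from any cause was 7.3%, or 3 of 41; 24 × 3/41 = 1.8. Neither ALT nor AST is on the list of drug-related Grade 3/4 events at 5% or more. Since 5% of 41 is 2.05, each had at most 2 cases. If these were different children, the ceiling is 4 of 41, and 24 × 4/41 = 2.3. This includes Grade 4 cases, which stop treatment and do not restart.

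**The case against.** **The table is headed as a recommendation and restart is discretionary.** True of whether to restart. The size of the step is a stated number, and Section 6.5 says the advice is to be followed.

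**A specific rule overrides a general one, so Table 6.5.1 simply governs.** If so, the contradiction with Section 6.1 goes, but the result is still a dose below the lowest paediatric level in the bands above, with no reason given for a 67% cut in the smallest children against 25% in adults.

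**After liver toxicity, too low a dose is the safer error.** This has force, and it limits the seriousness. It does not help where Section 6.1 is followed instead and the dose stays unchanged.

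**A one-level paediatric cut is weaker than the adult cut in large adolescents.** This stands. With a 20 mg step, an adolescent on 160 mg would restart at 140 mg (-12.5%), where an adult restarts at 120 mg. The documents do not show that the smaller cut is enough, so the depth is a clinical choice for the sponsor.

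**Stronger readings that the documents do not support.**

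- A reader might infer that a child could be given 0 mg, because 40 - 40 = 0 for a child of 0.650-0.694 m² already at level -1. The 20 mg floor in Section 5.4 rules that dose out; the case shows only that the subtraction has no valid answer there.
- A reader might take the 34.1% dose-reduction figure from phase I as the frequency. It covers all causes and all four dose levels.
- A reader might take the width of the BSA bands as a share of patients. The documents give no BSA distribution.
- A reader might infer that 20 mg steps cannot be dispensed. Section 8.3 describes only a 40 mg tablet, but nothing shows that another strength was unavailable.

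**Conclusion.** The point holds for patients under 18 who are restarted after a first drug-related Grade 3 ALT/AST rise. From level 0, the 40 mg cut is below level -1 at every BSA and below level -2 at 0.650-1.097, 1.167-1.341, 1.500-1.585 and from 2.167 m². The largest effects are 60 to 20 mg (-67%) and 80 to 40 mg (-50%).

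Table 6.1.2 cannot stand in as written. Level -1 equals level 0 at 0.695-0.853, 0.973-1.097, 1.250-1.341, 1.528-1.585, 1.806-1.829 and from 2.084 m². In those bands the one-level step in Table 6.2 also changes nothing, so the rounding fault reaches beyond liver tests.

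The results assume that the child is still on the starting dose and that rounding is as stated. Few patients are likely to meet the liver rule: about 2.3 of 24 at the drug-related ceiling, even if all of cohorts D and E were children. No endpoint, sample size or error rate is touched. It should be fixed because a paediatric safety rule ought to give one valid dose. The wrong table number in Section 6.5 and the unstated source of 20 mg steps are clerical and not part of this finding.

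**What to change.** 1. In Table 6.5.1 keep the 40 mg cut for adults and add a line: patients under 18 reduce by one dose level in Table 6.1.2. If a deeper liver cut is wanted, for example 120 mg for adolescents on 160 mg to match adults, state it as a paediatric level.

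2. Replace Table 6.1.2 itself with a BSA-to-mg table, and align Table 5.4 with it. Changing Table 5.4 alone would leave two values for level -1.

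| BSA (m²) | Level 0 (mg) | Level -1 (mg) | Cut |
|---|---|---|---|
| 0.650-0.853 | 60 | 40 | 33% |
| 0.854-1.097 | 80 | 60 | 25% |
| 1.098-1.341 | 100 | 80 | 20% |
| 1.342-1.585 | 120 | 100 | 17% |
| 1.586-1.829 | 140 | 120 | 14% |
| 1.830 and over | 160 | 140 | 12.5% |

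3. State level -2 for each band. In the lowest band a second 20 mg step gives 20 mg (23-31 mg/m²), so say whether these children go to 20 mg or stop.

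The cost is one added line, one replacement table and one aligned table in the next amendment, plus a clinical decision on level -2 and on adolescents at 160 mg. Endpoints, sample size and visits do not change.

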### **6.6 Prevention/management strategies for diarrhea**

Diarrhea can be a common side effect of regorafenib. The preventive/management strategies for diarrhea should be consistent with local standards (e.g., anti-diarrheals and optimized hydration status).

Anti-diarrheal medications may be introduced if symptoms occur. Previous trials have shown that the diarrhea could be managed with **loperamide**. The recommended dose of loperamide is 4 mg at first onset, followed by 2 mg every 2 to 4 hours until diarrhea-free for 12 hours.

## **7. ADVERSE EVENTS: LIST AND REPORTING REQUIREMENTS**

Adverse event (AE) monitoring and reporting is a routine part of every clinical trial. The following list of AEs (Section 7.1) and the characteristics of an observed AE (Section 7.2) will determine whether the event requires expedited reporting **in addition** to routine reporting. For routine reporting it is expected that all adverse events grade 3 or greater are recorded.

## **7.1 Adverse Event and Laboratory Abnormalities**

### **7.1.1 Clinical AEs**

#### **7.1.1.1 Definition of Adverse Events**

Per the International Conference of Harmonisation (ICH), an AE is any untoward medical occurrence in a patient or clinical investigation subject administered a pharmaceutical product and which does not necessarily have a causal relationship with the treatment. An AE can therefore be any unfavorable and unintended sign (including an abnormal laboratory finding), symptom, or disease temporally associated with the use of a medicinal (investigational) product, whether or not considered related to the medicinal (investigational) product. Pre-existing conditions which worsen during a study are to be reported as AEs.

#### **7.1.1.2 CTCAE term (AE description)**

The descriptions found in the revised NCI Common Terminology Criteria for Adverse Events (CTCAE) version 4.03 will be utilized for AE reporting. All appropriate treatment areas should have access to a copy of the CTCAE version 4.03. A copy of the CTCAE version 4.03 can be downloaded from the CTEP web site (<http://ctep.cancer.gov>).

